## 6.2 Exclusion criteria

*Subjects who exhibit any of the following conditions at screening will not be eligible for admission into the study.*

- 6.2.1 Subjects who are treated for bilateral breast cancer resection procedure.
- 6.2.2 Subjects who are pregnant at the time of diagnosis of their breast cancer; this exclusion is necessary because the teratogenic properties of LUM015 are unknown. Because there is an unknown but potential risk of adverse events in nursing infants secondary to treatment of the mother with LUM015, breastfeeding should be discontinued if the mother is treated with LUM015.
- 6.2.3 Subjects who are sexually active and not willing/able to use medically acceptable forms of contraception (hormonal or barrier method of birth control, abstinence) upon entering the study and for 60 days after injection of LUM015. Should a woman become pregnant or suspect she is pregnant while participating in this study, she should inform her treating physician immediately. Breast cancer patients are routinely advised against becoming pregnant during treatment, so this requirement does not differ from standard of care.
- 6.2.4 Subjects who have taken an investigational drug within 30 days of enrollment.

LUMICELL CONFIDENTIAL

This document is confidential. Do not disclose or use except as authorized.

- 6.2.5 Subjects with prolonged QTc interval defined as greater than 480 ms.
- 6.2.6 Subjects who will have administration of methylene blue or any dye for sentinel lymph node mapping on the day of the surgery prior to imaging the lumpectomy cavity with the LUM Imaging Device.
- 6.2.7 Subjects who have not recovered from adverse events due to other pharmaceutical or diagnostic agents.
- 6.2.8 Subjects with uncontrolled hypertension defined as persistent systolic blood pressure > 180 mm Hg, or diastolic blood pressure > 110 mm Hg; those subjects with known HTN should be stable within these ranges while under pharmaceutical therapy.
- 6.2.9 History of allergic reaction to polyethylene glycol (PEG).
- 6.2.10 History of allergic reaction to any oral or intravenous contrast agents.
- 6.2.11 Uncontrolled intercurrent illness including, but not limited to ongoing or active infection, symptomatic congestive heart failure, unstable angina pectoris, cardiac arrhythmia, COPD or asthma requiring hospitalization within the past 12 months, or psychiatric illness/social situations that would limit compliance with study requirements.
- 6.2.12 HIV-positive individuals on combination antiretroviral therapy are ineligible because of the potential for pharmacokinetic interactions with LUM015.
- 6.2.13 Any subject for whom the investigator feels participation is not in the best interest of the subject.
- 6.2.14 Subjects undergoing a second lumpectomy procedure because of positive margins in a previous surgery prior to entering this study.
- 6.2.15 Subjects with prior ipsilateral breast cancer surgeries, mastectomies, breast reconstructions or implants.
- 6.2.16 Subjects who have undergone a surgical biopsy for any reason in the ipsilateral breast performed less than 2 years prior to enrollment of this study.
- 6.2.17 Subjects with prior ipsilateral reduction mammoplasties (breast reductions) performed less than 2 years prior to enrollment to this study.
- 6.2.18 Subjects previously treated with systemic therapies to treat the cancer to be removed during this clinical investigation, such as neo-adjuvant chemotherapy or hormonal therapy.
- 6.2.19 Subjects undergoing breast conserving surgery whose resected specimen will be evaluated with frozen section.

LUMICELL CONFIDENTIAL

This document is confidential. Do not disclose or use except as authorized.

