## 7 SUBJECT ENROLLMENT

### 7.1 General guidelines for screening and enrollment

An investigator will confirm eligibility criteria and a member of the site study team will complete the protocol-specific eligibility checklist in the Case Report Form.

The site study team will document subject eligibility on the Screening and Enrollment form and notify Luminicell of a potential candidate for the study after the subject has been consented. For circumstances in which a potential candidate does not continue with study treatment or withdraws consent, the site study team should document the subject as “dropped” and document an explanation as to why the subject has not continued with the study.

The subject is not considered enrolled into the study until written Informed Consent is obtained and the investigational product has been administered (Study Day One).

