### 7.2 Enrollment process

The enrollment procedures are as follows:

1. Obtain written informed consent from the subject prior to the performance of any study related procedures or assessments.
2. Complete protocol-specific eligibility checklist and/or the screening questionnaire using the eligibility assessment documented in the subject's medical/research record. **To be eligible for registration in the study, the subject must meet each inclusion criteria and have none of the exclusion criteria listed on the eligibility checklist.**
3. Assign the subject a study subject ID number. The subject ID numbers at each site should follow the Luminicell assigned format as described at the Site Initiation Visit in compliance with the Case Report Form nomenclature. Numbers should follow a sequential order in accordance with subject enrollment at each site.
4. Notify Luminicell clinical team of eligible subject status and date of proposed surgery.

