## 10 STUDY CALENDAR

Baseline evaluations are to be conducted within 8 weeks ( $\pm$  3 days) prior to subject enrollment (Day 1). All baseline assessments must be performed prior to administration of any study agent. The study calendar below applies to all subjects injected with LUM015 including those that do not undergo imaging due to any reason, including a failure in the LUM Imaging Device initialization.

Task	Baseline evaluation/screening	Day 1 / Enrollment	$\sim$ 2-14 days after surgery	Routine follow up visit
LUM015 administration			X	
Informed consent	X			
History	X			
Concurrent meds	X			
Physical exam (Ht, Wt, VS)	X			
Surgery/intraoperative imaging		X		
Histology margin assessment			X	
EKG	X			
CBC	X			X
Serum chemistry a	X			X
Adverse event/adverse device effect evaluation		X		X
Tumor measurements	X			X
Radiologic evaluation	X			
B-HCG	X b			

a: Albumin, alkaline phosphatase, total bilirubin, BUN, calcium, chloride, glucose, potassium, total protein, SGOT [AST], SGPT [ALT], sodium.

b: Serum pregnancy test (women of childbearing potential).

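### The pregnancy exclusion in 6.2.2 is dated to cancer diagnosis, and the protocol text does not require a recent pregnancy test before LUM015 is injected

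*Protocol*

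**What the plan says.** Protocol 6.2.2 excludes "Subjects who are pregnant at the time of diagnosis of their breast cancer" and gives the reason directly: "this exclusion is necessary because the teratogenic properties of LUM015 are unknown". The lead-in to 6.2 applies its criteria at screening.

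Protocol 6.2.3 excludes sexually active women who are unwilling or unable to use "contraception (hormonal or barrier method of birth control, abstinence) upon entering the study and for 60 days after injection of LUM015". It also tells a woman who becomes pregnant, or suspects that she is, to inform her physician at once.

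The study calendar (section 10) has one pregnancy test, a B-HCG in the baseline column, footnoted "Serum pregnancy test (women of childbearing potential"). On timing it says "Baseline evaluations are to be conducted within 8 weeks", with a tolerance of 3 days either way, counted back from Day 1. It adds: "All baseline assessments must be performed prior to administration of any study agent". Under 7.1 a subject is "not considered enrolled into the study until written Informed Consent is obtained and the investigational product has been administered (Study Day One"), so Day 1 is the injection day.

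**The concern.** The reason for the exclusion is possible harm to a fetus from LUM015. The relevant moment is therefore the injection, but the criterion asks about the date of the cancer diagnosis. The B-HCG should cover the gap, yet it can be weeks old when the agent is given, and no criterion in 6.1 or 6.2 makes a negative result a condition of dosing.

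At stake is exposure of an unrecognised early pregnancy to an agent whose effect on the fetus the protocol calls unknown. Women of childbearing potential are expected in the study. Protocol 6.1.2 admits women from age 18, the calendar footnote provides for them, and SAP 4.1 tabulates menopausal status.

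**Working it through.** **Age of the test at injection.** The inputs are the 8-week baseline window and 3-day tolerance (section 10) and Day 1 as the day of administration (7.1).

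- Nominal: 8 × 7 = 56 days.
- Tolerance read as lengthening the window: 56 + 3 = 59 days.
- Tolerance read as shortening it: 56 − 3 = 53 days.

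Since Day 1 is the injection day, the length of the window is the greatest permitted age of the B-HCG at injection. The only other limit is that baseline items precede the agent. A site may therefore test much later, even on Day 1 before the injection. The documents do not give the interval that sites actually use.

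**What 6.2.2 covers, read literally.**

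- Pregnant at diagnosis: excluded.
- Conceived between diagnosis and screening: not excluded by 6.2.2. Applying the criteria at screening fixes when the question is asked, but the question is still about pregnancy at diagnosis.
- Conceived after screening: not reached by 6.2.2, because pregnancy at diagnosis cannot become true later. Protocol 8.6 reaches this woman through mandatory discontinuation on pregnancy, provided that the pregnancy is known.

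**Checks at dosing.** The administration sections (8.1 and 9.8) and the 11 numbered preparation and injection steps in Appendix A contain no pregnancy check. The Day 1 schedule of the Appendix D sub-study has none either.

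**What the other safeguards can detect.**

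- Contraception (6.2.3) is preventive. Step 1 of 7.2 reads "Obtain written informed consent from the subject prior to the performance of any study related procedures or assessments". If study entry means consent, contraception is required for the whole interval from B-HCG to injection. It does not exclude contraceptive failure, or a conception before consent that was too recent for the baseline test to show.
- Reporting (6.2.3) acts on a known or suspected pregnancy.
- Investigator discretion (6.2.13, and 8.4 for a safety concern or a change in condition) needs something to prompt it.
- Discontinuation (8.6) acts on a known pregnancy.

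Each lowers the risk. None detects an early pregnancy that neither the woman nor her physician suspects.

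**The case against.** The strongest reply is that the protocol already handles pregnancy by several routes, so the wording of 6.2.2 has little practical effect. A woman with a positive baseline test has already consented. The investigator can exclude her under 6.2.13, and 8.6 requires discontinuation for pregnancy and provides for removal before dosing. A serum B-HCG restricted to women of childbearing potential and done before any agent has no evident purpose except to act on a positive. This largely stands. The documents do not suggest that a woman with a known positive test would be injected.

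Two stronger readings are tempting, and the documents support neither.

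- A reader might combine 6.2.3 with 7.1 and infer that no contraception is required before injection, because enrolment is complete only once LUM015 is given. But 6.2.3 names study entry and the period after injection as separate points, and the first would add nothing if both meant injection. The criterion is applied at screening. Protocol 15.3 defines the safety population as those entering the study who are also injected, so entry can occur without injection. Study entry is best read as consent.
- A reader might infer that nothing in the trial confirms pregnancy status at dosing. Protocol 7.2 makes the eligibility checklist part of the enrolment process. That checklist, the case report form and the consent form are not available here, and local pre-operative testing is not described. The finding is limited to the protocol text.

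It is also fair to say that the number of women affected is unknown and probably small. What remains is that the criterion is tied to the wrong time point and no recency is set for the test.

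**Conclusion.** The point holds for the protocol text. Protocol 6.2.2 is dated to diagnosis although its reason concerns injection. The one scheduled B-HCG may be up to 56 days old at dosing (53 to 59 with the tolerance), and no dosing step checks pregnancy status. The residual risk is an unrecognised early pregnancy, from contraceptive failure or from a conception too recent for the baseline test.

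This rests on taking Day 1 as the injection day, as 7.1 states, and on the B-HCG being a baseline item only. It does not depend on the calendar's LUM015 administration row, which looks displaced in the extracted table. The share of women of childbearing potential among the maximum of 250 patients is not given, so the number at risk cannot be estimated.

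It is a cheap improvement to patient safety. It has no effect on endpoints, sample size or analysis.

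**What to change.** - Reword 6.2.2 to exclude women known to be pregnant at screening or with a positive pre-dose test.
- Move the existing B-HCG to a short window before injection, for example with the pre-operative bloods. The documents give no basis for a particular length, so the sponsor's clinical team should set it.
- Require a negative result before LUM015 is given to a woman of childbearing potential, and add this check to the dosing instructions.
- State in 6.2.3 that contraception starts at consent. This is only a clarification.

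The cost is a few lines of wording, a calendar footnote and one pre-dose check. The test is moved, not added, although a site that also wants a result at screening would need a second one. A late positive may occasionally disrupt a booked operation. Protocol 8.6 already says that subjects removed before dosing receive standard of care, are not counted and are replaced, so the sample size is protected.

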### 6.3 Inclusion of women, minorities and other underrepresented populations

As this study is to test the efficacy of an intraoperative imaging technology in female breast cancer subjects, all of the subjects will be women. Males with breast cancer (<1% of breast cancer patients) usually undergo mastectomy procedures and only rarely have lumpectomies, and thus would not be likely to be eligible for this study.

## 7 SUBJECT ENROLLMENT

### 7.1 General guidelines for screening and enrollment

An investigator will confirm eligibility criteria and a member of the site study team will complete the protocol-specific eligibility checklist in the Case Report Form.

The site study team will document subject eligibility on the Screening and Enrollment form and notify Luminicell of a potential candidate for the study after the subject has been consented. For circumstances in which a potential candidate does not continue with study treatment or withdraws consent, the site study team should document the subject as “dropped” and document an explanation as to why the subject has not continued with the study.

The subject is not considered enrolled into the study until written Informed Consent is obtained and the investigational product has been administered (Study Day One).

### 7.2 Enrollment process

The enrollment procedures are as follows:

1. Obtain written informed consent from the subject prior to the performance of any study related procedures or assessments.
2. Complete protocol-specific eligibility checklist and/or the screening questionnaire using the eligibility assessment documented in the subject's medical/research record. **To be eligible for registration in the study, the subject must meet each inclusion criteria and have none of the exclusion criteria listed on the eligibility checklist.**
3. Assign the subject a study subject ID number. The subject ID numbers at each site should follow the Luminicell assigned format as described at the Site Initiation Visit in compliance with the Case Report Form nomenclature. Numbers should follow a sequential order in accordance with subject enrollment at each site.
4. Notify Luminicell clinical team of eligible subject status and date of proposed surgery.

## 8 INTERVENTIONAL PLAN

### 8.1 LUM015 administration

The investigational imaging agent LUM015 will be administered at the hospital  $4 \pm 2$  hours prior to surgery. See section 9 for more details about the preparation and administration of LUM015.

LUMICELL CONFIDENTIAL

This document is confidential. Do not disclose or use except as authorized.

No investigational or commercial agents or therapies other than those described in this protocol may be administered with the intent to image the subject's malignancy intraoperatively.

As per IV injection standard of care, all subjects will be observed for signs of extravasation or allergic reaction following administration of LUM015 to monitor for adverse pharmacological activity related to the investigational agent. If extravasation is suspected or confirmed, the injection must be stopped immediately and reported to Luminicell. All study safety assessments will continue until the first post-operative visit (approximately 2-3 weeks after surgery).

If there is evidence that there was extravasation of the LUM015 injection, then that patient will be excluded from the efficacy cohort and the cohort used for training the surgeons. However, the patient will be included in the safety data analysis.

If the patient is experiencing an allergic reaction to LUM015 administration, the injection should be stopped immediately, and the following lab values should be obtained:

- Histamine
- Total Blood Complement
- Tryptase levels

The blood draw for each of these tests should be done as soon as possible after the start of the reaction and again at 30 minutes post start of the reaction. If an immediate blood draw is not possible, collect a 30-minute blood draw at minimum. Each blood specimen should be processed, packaged and shipped to the contracted central laboratory for this study. Specific instructions on collection, processing, and shipping can be found in the training materials associated with this study.

In case of an allergic reaction to LUM015, sites should not discard any residual drug remaining in the used syringe. This drug should be stored at -20 degrees C until a Luminicell representative notifies your site of how to proceed with the used syringe.

## 8.2 Imaging of the lumpectomy cavity walls and shaved cavity margins

For Phase C, the surgeon will perform the lumpectomy procedure according to his or her institution's standard of care practice as outlined in sections 5.4.1 to 5.4.3. After the standard of care procedure, the surgeon will have the option of using the LUM002 or the LUM003 depending on their preference and their assessment of likely incision and surgical cavity dimensions. Following the standard of care procedure, the surgeon will image the tumor bed in order to establish a normal tissue baseline for the thresholding algorithm. With the thresholding algorithm applied, the surgeon will then remove therapeutic shaves based on the recommendation of the LUM Imaging System. The surgeon will be limited to removing no more than 2 therapeutic shave for a given orientation (see section 5.3 for definitions of orientations). If the surgeon decides to take a different action than the one suggested by the LUM Imaging System, this is considered a protocol deviation. The surgeon must notify the computer operator or clinical coordinator for documenting the reason for not following the study procedures in the study worksheets. The

LUMICELL CONFIDENTIAL

This document is confidential. Do not disclose or use except as authorized.

surgeon has the option to record an image from the final cavity after the 2 therapeutic shaves are removed.

Also, ex vivo images of the non-margin side of shaved cavity margins will be recorded in the operating room after the in vivo portion of the imaging session is completed.

### 8.3 General concomitant medication

A complete listing of all medications (including non-prescription, vitamins, herbal products and essential oils) currently being taken on a regular basis prior to surgery will be obtained at screening and updated as needed at enrollment and at follow-up. Concomitant medications will be recorded in the medical record and case report form.

### 8.4 Duration of therapy

The imaging agent LUM015 will be injected as a single dose  $4 \pm 2$  hours prior to surgery. There is no recurrent administration of the imaging agent. The treatment ends after the surgery is completed. Subjects' participation in the study may be discontinued by the principal investigator at any time for any of the following reasons:

- unacceptable adverse event or adverse device effect
- administrative reasons, such as imaging agent no longer available
- subject noncompliance,
- safety concern,
- subject decides to withdraw from the study, or
- general or specific changes in the subject's condition render the subject unacceptable for further treatment in the opinion of the treating investigator.

### 8.5 Duration of follow-up

All study interventions will be completed at the end of the surgical procedure. All subjects will continue their enrollment until the first follow-up visit and will continue to be followed in the study until their medical team determines that no further surgical intervention is required. For example, if a patient needs a second surgery because of positive margins, the patient will remain enrolled in the study until the second surgery (whether a mastectomy or a lumpectomy re-excision) is performed, the pathology report is available and her medical team determines that no additional surgery is needed. When attending their first post-operative visit, a blood draw will be collected for a CBC (red blood cells, white blood cells and platelets) and serum chemistry (alkaline phosphatase, total bilirubin, BUN, calcium chloride, glucose, potassium, total protein, SGOT [AST], SGPT [ALT], sodium) tests to assess for possible adverse events. At the time of the visit, the patient will be interviewed to determine any potential adverse events. Subjects with adverse events that are determined to be possibly related to the investigational product will be followed until resolution or stabilization of the adverse event.

### 8.6 Criteria for removal from study

Subjects will be removed from study when any of the criteria listed in section 6.2 apply. The reason for study removal and the date the subject was removed must be documented in the study-specific case report form (CRF). A subject removed from the study will be given standard of care treatment.

LUMICELL CONFIDENTIAL

This document is confidential. Do not disclose or use except as authorized.

Subjects removed from the study prior to dosing with LUM015 will not be included in the total patient counts and will be replaced with a new subject.

Individual patients may be discontinued from the study by the Investigator or Luminell at any time if either determines that it is not in the best interest of the patient to continue (e.g., continuation in the study represents a serious medical risk to the patient). This may include, but is not limited to, the presence of serious, life-threatening adverse events, unanticipated adverse device effects, adverse events, or adverse device effects that are unacceptable in nature, severity, or frequency as assessed by the Investigator.

Patients must be discontinued if they become pregnant or withdraw consent. Patients may be discontinued due to noncompliance with the protocol. While patients will be encouraged to complete the study, they may voluntarily withdraw at any time.

In the event of unusual or life-threatening complications, participating investigators must immediately notify the Medical Monitor, [name], the Principal Investigator, and the Luminell study monitor.

